16.1.3 Serious Adverse Events

A serious adverse event (SAE) is any adverse event occurring at any dose that results in any of the following outcomes:

- death,
- life-threatening (places the subject, in the view of the investigator, at immediate risk of death from the reaction as it occurred),
- inpatient hospitalization or prolongs existing hospitalization,
- persistent or significant disability/incapacity (a substantial disruption of a person's ability to conduct normal life functions),
- birth defect/congenital anomaly,
- or any important medical event that may not result in prior listed outcomes but, based upon appropriate medical judgment, may jeopardize the subject, and may require medical or surgical intervention to prevent one of the prior listed outcomes.

16.1.4 Treatment of Investigational Product Overdose

No maximum tolerated dose (MTD) was reached in the dose escalation study of pazopanib administered as a single agent at repeated doses of up to 2000mg/day (Study VEG10003). Systemic exposure to pazopanib at steady-state appeared to plateau at doses greater than 800 mg once daily. Increases in the daily pazopanib dose above 800 mg in the fasted state resulted in a small or no increase in mean systemic exposure to pazopanib.

In the event of pazopanib overdose (defined as administration of more than the protocol-specified dose), the Study Chair should contact the Novartis Pharmaceuticals Study Physician. If the event takes place at Yale, the Principal Investigator will immediately notify the Study Chair.

Decisions regarding pazopanib dose modifications or interruptions will be made by the Study Chair in consultation with the Novartis Pharmaceuticals Study Physician, and with the Yale Investigator, if applicable, based on the clinical evaluation of the subject.

Following an overdose, additional monitoring of the subject for AEs/SAEs and laboratory abnormalities should be considered. A plasma sample for pharmacokinetic analysis for pazopanib and NSAI may be requested by the Novartis Pharmaceuticals Study Physician on a case-by-case basis. This plasma sample should be collected as soon as possible, but within 7 days from the date of the last dose of study drug.

Information regarding the quantity of the excess dose, as well as the duration of overdosing, should be documented in the eCRF.

NSAI overdose is very rare; currently there is no standard guideline on the management of NSAI overdose.

16.2 Adverse Event Reporting Procedures

16.2.1 Data and Safety Monitoring Plan

Oversight and Monitoring Plan

The UCSF- Helen Diller Family Comprehensive Cancer Center (HDFCCC) Data Safety Monitoring Committee (DSMC) is responsible for monitoring data quality and patient safety for all HDFCCC institutional clinical studies. A summary of DSMC activities for this study at UCSF includes:

- Review of subject data
- Review of suspected adverse reactions considered “serious”
- Monitoring every six months (depending on study accrual)
- Minimum of a yearly audit

At Yale, monitoring takes place after the first two patients and then 10% annually thereafter. The monitoring plan is set at the scientific review committee meeting as determined by the local PRC (Protocol Review Committee).

Monitoring and reporting Guidelines

All institutional Phase 2 therapeutic studies are designated with a moderate risk assessment. The data is monitored every six months, with twenty percent of the subjects monitored (or at least three subjects if the calculated value is less than three).

The UCSF Coordinating Center provides administration, data management, and organizational support for the participating sites in the conduct of a multicenter clinical trial. The UCSF Coordinating Center will also coordinate monthly conference calls with the participating sites to communicate the review of adverse events, safety data, and other study matters.

The Principal Investigator at the UCSF Coordinating Center will hold the role of Study Chair. The Study Chair is responsible for the overall conduct of the study and for monitoring its safety and progress at all participating sites. The Study Chair will conduct continuous review of data and patient safety and discuss at monthly study group or site committee meetings at UCSF, and during monthly teleconferences with Yale. At UCSF Site Committee, the results of each patient's treatment are discussed and the discussion is documented in the minutes. The discussion will include the number of patients, significant toxicities as described in the protocol, doses adjustments, and observed responses. All grade 3 or above AEs and SAEs will be entered in the UCSF Helen Diller Family Comprehensive Cancer Center CTMS database.

Multicenter communication

The UCSF Coordinating Center provides administration, data management, and organizational support for the participating sites in the conduct of a multicenter clinical trial. The UCSF Coordinating Center will also coordinate, at minimum, quarterly conference calls with the participating sites or more frequently as needed to discuss risk assessment. The following issues will be discussed as appropriate:

- Enrollment information
- Adverse Events (i.e. new adverse events and updates on unresolved adverse events and new safety information)
- Protocol Violations
- Other issues affecting the conduct of the study

Adverse events reporting to the DSMC will include reports from both the UCSF Coordinating Center, as well as the participating sites. The DSMC will be responsible for monitoring all data entered in OnCore® at the UCSF Coordinating Center and the participating sites. The data (i.e. copies of source documents) from the participating sites will be faxed over to the UCSF Coordinating Center prior to the monitoring visits in order for the DSMC to monitor the participating site's compliance with the protocol, patient safety, and to verify data entry.

Review and Oversight Requirements

Adverse Event Monitoring

Adverse Events (AEs) will be recorded on the UCSF Helen Diller Family Comprehensive Cancer Center CTMS database, all grade 3 and above expected and unexpected AEs will be recorded and updated at each visit.

All Grade 3-5 adverse events entered into OnCore® will be reviewed on a monthly basis at the UCSF Site Committee meetings. All clinically significant adverse events must be reported to the UCSF Coordinating Center by the participating sites within **10 business days** of becoming aware of the event or during the next scheduled quarterly conference call, whichever is sooner. The UCSF Site Committee will review and discuss the selected toxicity, the toxicity grade, and the attribution of relationship of the adverse event to the administration of the study drug(s) from the UCSF Coordinating Center and the participating sites.

In addition, all suspected adverse reactions considered “serious” must be entered in OnCore® and reported to the UCSF Coordinating Center within **1 business day**. The suspected adverse reactions considered “serious” will be reviewed and monitored by the Data and Safety Monitoring Committee on an ongoing basis and discussed at the DSMC meeting, which take place every six (6) weeks.

If a death occurs during the treatment phase of the study or within 30 days after the last administration of the study drug(s) and is determined to be related either to the investigational drug or any research related procedure, the Study Chair at the UCSF Coordinating Center or the assigned designee must be notified within **1 business day** from the participating site(s) and the Study Chair must then notify the DSMC Chair or qualified alternate within **1 business day** of this notification. The contact may be by phone or e-mail.

16.2.2 Serious Adverse Event Reporting

Serious Adverse Event reporting will be in accordance with the UCSF-Committee on Human Research and the Yale School of Medicine Human Investigation Committee guidelines and Code of Federal Regulation Title 21 Volume 5 Part 312.32.

UCSF CHR website for guidance in reporting serious adverse events
http://www.research.ucsf.edu/chr/Guide/Adverse_Events_Guidelines.pdf

FDA website for guidance in reporting serious adverse events
<http://www.accessdata.fda.gov/scripts/cdrh/cfdocs/cfcfr/CFRSearch.cfm?fr=312.32>

MedWatch forms and information:
<http://www.fda.gov/medwatch/getforms.htm>

Serious Adverse events will be reported on the MedWatch form. The date the SAE was sent to all required reporting agencies will be documented on the UCSF Helen Diller Family Comprehensive Cancer Center CTMS database.

Participating Sites Reporting to Study Chair (UCSF)

In addition to complying with all applicable regulatory reporting laws and regulations, each site will report the following information in writing to the Sponsor-Investigator within one business day of the Investigator's awareness of occurrence:

- All SAEs
- Reports of pregnancy exposure (pregnancy encompasses the entire course of pregnancy and delivery, perinatal and neonatal outcomes, even if there were no abnormal findings; both maternal and paternal exposure is collected);
- Reports of lactation exposure;
- Overdose (with or without an SAE);
- Abuse (use for non-clinical reasons with or without an SAE);
- Inadvertent or accidental exposure; and
- Follow-up information regarding any of the above.
- The participating investigator should include his or her assessment of the causal relationship between each SAE and the Grantor product.

Reports will include the cover page provided, and reference the Protocol Number.

A copy of the report should be sent to the coordinating center CRC at UCSF. Information will be provided.

Study Chair (UCSF) AE reporting to Novartis Pharmaceuticals

Any serious adverse events which occur during the clinical study or within 5 days of receiving the last dose of study medication, whether or not related to the study drug, must be reported by the Study Chair. In addition, any SAEs which occur as a result of protocol specific diagnostic procedures or interventions must also be reported.

	Initial Reports		Follow-up Information on a Previous Report	
Type of Event	Time Frame	Documents	Time Frame	Documents
All SAEs	24 hours	SAE data collection tool	24 hours	Updated SAE data collection tool
Pregnancy	2 weeks	Pregnancy Notification Form	2 weeks	Pregnancy Follow up Form
Liver chemistry abnormalities:				

ALT: >3.0 x ULN with concomitant elevation in bilirubin ^a (defined as total bilirubin \geq 2.0 x ULN with direct bilirubin >35%) or with hypersensitivity symptoms (e.g., fever, rash).	24 hours	SAE data collection tool. ^b Liver Event Case Report Form (CRF) and liver imaging and/or biopsy CRFs if applicable	24 hours	Updated SAE data collection tool. ^b Updated Liver Event CRF
ALT >8.0 x ULN without bilirubin elevation (defined as total bilirubin $<$ 2.0 x ULN or direct bilirubin \leq 35%) and without hypersensitivity symptoms (e.g., fever, rash)	24 hours	SAE data collection tool. Liver Event CRF ^b	24 hours	Updated SAE data collection tool. Updated Liver Event CRF ^b

- a. Bilirubin fractionation should be performed if testing is available. If testing is unavailable and a subject meets the criterion of total bilirubin \geq 2.0 x ULN, then the event should be promptly reported as defined.
- b. Liver event documents should be completed as soon as possible.

All Events must be reported to Novartis within 24 hours of learning of its occurrence. Information about all SAEs is collected and recorded on a Serious Adverse Event Report Form; all applicable sections of the form must be completed in order to provide a clinically thorough report. The investigator must assess and record the relationship of each SAE to each specific study treatment (if there is more than one study treatment), complete the SAE Report Form in English, and send the completed, signed form by **fax within 24 hours to the oncology Novartis DS&E department with the provided FAX cover sheets.**

- Novartis DS&E Oncology Department - [REDACTED]

SAEs brought to the attention of the Study Chair at any time after cessation of pazopanib and considered by the Study Chair to be related or possibly related to pazopanib must be reported to Novartis Pharmaceuticals if and when they occur. Additionally, in order to fulfill international reporting obligations, SAEs that are related to study participation (e.g., procedures, invasive tests, change from existing therapy) or are related to a concurrent medication will be collected and recorded from the time the subject consents to participate in the study until he/she is discharged.

Review of Adverse Event Rates

If the study has an increase of unexpected or expected Adverse Event grade 3 or 4 above the rate reported in the Investigational Brochure or package insert, the increase rate of AEs will be reported by the Study Chair to the UCSF DSMC at the time of Identification. The UCSF DSMC Chair and Study Chair will discuss the finding and proceed with a written course of action. If at any time the Study Chair stops enrollment or stops the study due to safety issues the UCSF DSMC Chair must be notified within 24 business hours via e-mail. The UCSF DSMC must receive a formal letter within 10 business days and the CHR must be notified.

If any of the above action occurs in a multiple-institutional clinical trial coordinated by the UCSF-CCC, the Study Chair will insure that all participating sites are notified.

Data and Safety Monitoring Committee Contacts:

DSMC Chair: [REDACTED]

[REDACTED]

Email [REDACTED]

Box [REDACTED]

DSMC Monitors

[name]

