16.0 Reporting Adverse Drug Reactions

16.1 Adverse Event Definitions

16.1.1 Clinical Adverse Events

A clinical adverse event is any unfavorable or unintended sign, symptom or disease temporally associated with the use of the study drug occurring in a research patient treated with the study drug during treatment or post-treatment follow-up period, regardless of causality assessment. This includes adverse clinical or laboratory findings, intercurrent illness, or an exacerbation or progression of a disease/condition present at baseline.

An adverse event is unexpected if it is not listed in the current labeling for the study drug. An adverse event is considered non-serious if it does not meet any of the serious criteria below.

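### The adverse-event-rate trigger in Section 16.2.2 names Grade 3 or 4 only, so an event first recorded as fatal does not add to the rate that obliges a DSMC report and a written response

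*Combined protocol and SAP*

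**What the plan says.** The rule stands under Review of Adverse Event Rates in Section 16.2.2. Its condition is "If the study has an increase of unexpected or expected Adverse Event grade 3 or 4 above the rate reported in the Investigational Brochure" or the package insert. When the condition is met, the Study Chair reports the increase to the UCSF DSMC once it is identified, and "The UCSF DSMC Chair and Study Chair will discuss the finding and proceed with a written course of action". The rule applies to expected and unexpected events alike, has no relatedness filter, gives no numerical margin, and does not say whether rates are compared by event type or pooled.

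Section 9.2 adopts CTCAE version 4.0. On that scale death is a separate Grade 5, as the diarrhea table in Appendix III shows.

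Elsewhere the plan includes Grade 5. Section 16.2.1 (Adverse Event Monitoring) has events of Grade 3 and above recorded, and its sentence on the monthly Site Committee review begins "All Grade 3-5 adverse events entered into" the trial database.

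**The concern.** Read literally, the rule responds to a severe event that the patient survives and not to the same event when it is first recorded as fatal. The wider grade range in Section 16.2.1 suggests a drafting slip, not a reasoned exclusion.

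It matters because I find no other rate-based safety rule in the protocol. Section 12.4 gives a single enrollment hold after the fifth patient, and Section 10.1 lets the Study Chair stop for significant toxicity without a threshold. Section 1.2 reports that deaths from several causes, among them gastrointestinal hemorrhage, bowel perforation, myocardial infarction and cerebrovascular accident, were more common with pazopanib than with placebo in the renal cell trial. In a single-arm study of metastatic disease, whether a death is related is a judgment made without a control group. A rate comparison that ignores attribution is a useful check on that judgment, and it should not leave out the worst outcome.

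**Working it through.** The trigger carries no numerical threshold, so there is no stated figure to reproduce. The check has two parts: trace where a fatal event goes, then see whether the wording can change the trigger at this sample size.

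**Routes for a fatal event**

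- *Death judged related.* Section 16.2.1 covers a death on treatment, or within 30 days of the last dose, that "is determined to be related either to the investigational drug or any research related procedure". The site has one business day to tell the Study Chair, who has one more to tell the DSMC Chair: 1 + 1 = 2 business days. No rate comparison or written response is attached.
- *Serious suspected reaction.* The DSMC reviews it "on an ongoing basis and discussed at the DSMC meeting, which take place every six (6) weeks". This route also depends on suspicion of a drug cause.
- *Any SAE, related or not.* Under Section 16.2.2, sites report it to the Study Chair within one business day. This is not a notice to the DSMC.
- *General oversight.* The DSMC "is responsible for monitoring data quality and patient safety for all HDFCCC institutional clinical studies". Section 16.2.1 (Multicenter communication) also makes it responsible for monitoring all data entered in OnCore at the coordinating center and the participating sites, and Section 13.0 requires entry within a week of each visit. No deadline for DSMC action is given. Sampled monitoring is slower: "The data is monitored every six months, with twenty percent of the subjects monitored".

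So a death not judged related is known to the Study Chair quickly and lies within the DSMC's remit, but no timed DSMC notice is stated for it. No route adds any death to the Section 16.2.2 rate.

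**Can the wording change the trigger?**

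Inputs: 30 enrolled and 27 evaluable (Section 12.7); 14 in the first stage (Section 12.2); a list of uncommon events at 1% or less, including bowel perforation (Section 1.2); Grade 3/4 diarrhea in about 4% (Appendix III).

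Assumptions: these figures stand in for the brochure and package insert, which are not in the documents; rates are compared by event type; the event counts are hypothetical. Counted rate = events counted / patients.

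| Hypothetical events | Patients | Reference | Counting Grade 3 or 4 | Counting Grade 3 or higher |
|---|---|---|---|---|
| One bowel perforation, first recorded as fatal | 30 | at most 1% | 0/30 = 0%: not met | 1/30 = 3.3%: met |
| One diarrhea event, first recorded as fatal | 14 | about 4% | 0/14 = 0%: not met | 1/14 = 7.1%: met |
| One Grade 3 or 4 and one fatal diarrhea event | 30 | about 4% | 1/30 = 3.3%: not met | 2/30 = 6.7%: met |
| The same two events | 27 | about 4% | 1/27 = 3.7%: not met | 2/27 = 7.4%: met |

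Two checks on the references:

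- The 1% figure carries no grade. A rate restricted to Grade 3 or 4, or to Grade 3 or higher, can only be equal or lower, so the first row stands.
- The 4% figure covers Grade 3/4. A like-for-like reference would add fatal diarrhea, whose rate the documents do not give. The two-event rows still change if that rate is below 6.7 − 4 = 2.7 percentage points at 30 patients, or 7.4 − 4 = 3.4 points at 27.

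If event types are pooled, each fatal event left out lowers the counted rate by 1/30 = 3.3 points at 30 patients, or 1/14 = 7.1 points at 14.

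**The case against.** The best counter-argument is that deaths are handled elsewhere, and faster. This largely stands. Someone reading the rate rule alone might infer that fatal events escape the DSMC or go unmonitored. The documents do not support that: related deaths have a dedicated notice, serious suspected reactions have ongoing review, all entered data are within the DSMC's remit, and the Study Chair, who applies the rate rule, hears of every SAE within one business day.

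Second, the worked examples are known pazopanib toxicities. Fatal cases would probably be judged related and reach the DSMC Chair by the death route. That is fair. The examples show how the count behaves, not how often an unrelated death would be missed, and the documents give no basis for estimating that.

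Third, many fatal events would first be recorded at Grade 3 or 4, because records are updated at each visit, and would already have counted. This also stands, but the text states no such counting rule, and it does not help when the first recorded grade is 5.

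Fourth, Grade 3/4 matches the way the protocol mostly reports severe toxicity, with deaths listed apart. This is a reason to align the reference rate with the count. It is not a reason to leave deaths out of both.

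**Conclusion.** The point holds on the plain text: an event first recorded as Grade 5 does not add to the rate that obliges a DSMC report and a written response. The gap is small. It is confined to the formal rate comparison and the response that follows, and it matters chiefly for deaths not judged related. It is still worth correcting, because with about 30 patients one uncounted event can decide whether the trigger is met, and the correction is a change of phrase.

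The textual finding needs no assumption beyond a literal reading of the grade range; a lenient reader could take the phrase as shorthand for severe events, but nothing in the text says so. The size of the effect rests on stand-in reference rates, comparison by event type and hypothetical counts.

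**What to change.** In the Review of Adverse Event Rates text of Section 16.2.2:

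1. Replace the Grade 3 or 4 condition with Grade 3 or higher.
2. Count each event once, at its highest grade.
3. Compare with the brochure or package-insert rate on the same grades. Where the source lists Grade 3/4 rates and deaths separately, add its reported fatal events to the reference.
4. Exclude only deaths recorded as breast cancer progression with no other Grade 3 or higher adverse event contributing. Some exclusion is needed because Section 16.1.1 counts as an adverse event "an exacerbation or progression of a disease/condition present at baseline". It should stay this narrow, since a broader one would bring back the attribution filter that the rate rule avoids.

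The cost is a recorded judgment for each death, which the monthly Site Committee review can take on, and a trigger that is met slightly more often. No enrollment pause is proposed; the same part of Section 16.2.2 already covers the Study Chair stopping enrollment for safety.

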18.0 Appendices

Appendix I: ECOG Performance Status

ECOG PERFORMANCE STATUS*	
Grade	ECOG
0	Fully active, able to carry on all pre-disease performance without restriction
1	Restricted in physically strenuous activity but ambulatory and able to carry out work of a light or sedentary nature, e.g., light house work, office work
2	Ambulatory and capable of all selfcare but unable to carry out any work activities. Up and about more than 50% of waking hours
3	Capable of only limited selfcare, confined to bed or chair more than 50% of waking hours
4	Completely disabled. Cannot carry on any selfcare. Totally confined to bed or chair
5	Dead

* As published in Am. J. Clin. Oncol.:

The ECOG Performance Status is in the public domain therefore available for public use. To duplicate the scale, please cite the reference above and credit the Eastern Cooperative Oncology Group, Robert Comis M.D., Group Chair.

